### Step 4- EDS evaluation (20 mins)

Subjects will be evaluated for hypermobile EDS (hEDS) and hypermobility spectrum disorders (HSD) by [name] or a colleague trained to diagnose EDS using a standardized form.

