# 1.0 Objectives

# 1.1 Study Objectives

The overall goal of this study is to investigate the impact of orthostatic stress on cognitive function in postural tachycardia syndrome (POTS), and to assess the prevalence of Hypermobile Ehlers-Danlos Syndrome (hEDS) and Hypermobility spectrum disorders (HSD) in patients with POTS. **This study will be performed in a large cohort (100 POTS patients) at the Dysautonomia International Conference in Nashville, TN June 22-24, 2018**. Healthy control subjects will be enrolled at Penn State Hershey Medical Center. The central hypothesis is that active standing in POTS worsens cognitive function and related to joint hypermobility. We will test this hypothesis in the following two specific aims:

Aim 1: Determine impact of orthostatic stress on cognition in POTS. Hypothesis 1: Active standing in POTS worsens cognitive function. Cognitive function will be assessed in the supine and standing postures using a short battery of cognitive tests. These tests examine aspects of cognition known to be impaired in POTS patients including executive function (Stroop word color test), attention (CogState Identification test), and working memory (CogState two-back test). Aim 1 will be performed in POTS patients and in healthy subjects.

Aim 2: Determine the prevalence hEDS and HSD in POTS. We will assess patients for hEDS and HSD using a questionnaire and physical exam based on the new guidelines. Aim 2 will only be performed in POTS patients.

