# 1.2 Primary Study Endpoints

Our primary endpoints are the scores on the cognitive tests and the Beighton score.

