### **Joint Hypermobility in POTS**

The high prevalence of hEDS in POTS was first recognized by [name], et al. in 1999. He found that about 60% of patients with chronic fatigue syndrome and orthostatic intolerance had joint hypermobility but this study was only conducted in 12 subjects. One small study found that 29% of pediatric POTS patients have joint hypermobility. Larger, questionnaire based studies have estimated that 30-40% of POTS patients have been diagnosed with EDS. But because there are very few geneticists that specialize in EDS and most physicians who evaluate POTS patients do not evaluate for EDS. The true prevalence of hEDS in POTS has not been evaluated. Furthermore, HSD is a new diagnosis defined in 2017, and no study to date has attempted to determine the rate of HSD in POTS.

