# 7.2 Study Procedures

## Step 1- Questionnaires (15 mins)

Subjects will answer questions about their POTS diagnosis, co-morbid conditions (including hEDS), and current medications, and family history. Participants will also complete standardized questionnaires including the Orthostatic grading scale, Compass 31, RAND-36, and Fatigue-VAS. All questions will be answered on tablets and data will be entered directly into REDCap. Participants will have the option to complete the questionnaires during the study visit on a tablet or after their study visit by providing their email address. A link to the questionnaires in REDCap will be emailed to participants to complete after the study visit.

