### 7.3 Duration of Participation

Study participation will take approximately 1 hour per subject. Subjects may opt to complete questionnaires up to 1 month after their study visit. Only POTS patients will complete questionnaires.

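### Nothing in the plan keeps the Step 4 examiner from knowing a prior EDS diagnosis before scoring the Beighton and other physical signs

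*Combined protocol and SAP*

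**What the plan says.** Section 1.2 states: "Our primary endpoints are the scores on the cognitive tests and the Beighton score". For Aim 2, Section 1.1 states: "We will assess patients for hEDS and HSD using a questionnaire and physical exam based on the new guidelines". Section 7.1 says the Aim 2 questionnaire and exam data are to be given as percentages.

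The procedures are in Section 7.2. Under Step 1, "Subjects will answer questions about their POTS diagnosis, co-morbid conditions (including hEDS), and current medications, and family history". On recording, "All questions will be answered on tablets and data will be entered directly into REDCap". The step need not be finished at the visit: Section 7.3 says "Subjects may opt to complete questionnaires up to 1 month after their study visit". Step 4 is a single sentence, "Subjects will be evaluated for hypermobile EDS (hEDS) and hypermobility spectrum disorders (HSD) by" a named person or a trained colleague, on a standardised form. The form is not among the documents.

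On how common a prior label may be, Section 2.2 (Joint Hypermobility in POTS) says: "Larger, questionnaire based studies have estimated that 30-40% of POTS patients have been diagnosed with EDS".

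No section masks the examiner, limits who may see the Step 1 answers, sets the order of signs and history, or provides a second rater or agreement check.

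**The concern.** Scoring a joint sign near its cut-off takes some judgement. An examiner who already knows that a patient carries an EDS diagnosis may resolve borderline signs in its favour. The knowledge can arrive in two ways: from Step 1 answers, when these are completed before the exam, or from the patient in conversation. The plan closes neither route.

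What the exam adds over a questionnaire survey is a direct measurement. To the extent that signs are read in the light of an existing label, the Beighton score is not an unprompted measurement, and part of the hEDS percentage repeats earlier diagnoses. If hEDS and HSD are counted as exclusive categories, moving a borderline patient up to hEDS would also lower the HSD percentage. Unlike sampling error, this kind of error does not shrink as more patients are enrolled.

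**Working it through.** The plan gives no precision or error figure on this point, so there is none to reproduce. The check has two parts.

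**1. What the documents contain.** The sections on objectives, endpoints, procedures, statistics and data monitoring were read for any safeguard.

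- Partial safeguards found: a trained examiner, a standardised form, tablet entry into REDCap, and the option to complete questionnaires after the visit.
- Not found: masking of the examiner, restricted access to Step 1 answers, an order of scoring, or a second rating.

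**2. How large the effect could be.** This is an illustration, and two of its inputs are assumed.

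- n = 100 POTS patients, the maximum in Section 8.1.
- L = share arriving with a prior EDS label, 0.30 to 0.40 (Section 2.2). This figure is for EDS, not hEDS specifically, and comes from other cohorts. Using it here is an assumption.
- f = share of labelled patients who would be negative under masked scoring, assumed 0.2 to 0.5.
- u = share of those called positive because the label is known, assumed 0.1 to 0.5.

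Upward shift in the hEDS percentage, in points = 100 × L × f × u.

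| L | f | u = 0.1 | u = 0.25 | u = 0.5 |
|---|---|---|---|---|
| 0.30 | 0.2 | 0.6 | 1.5 | 3.0 |
| 0.30 | 0.5 | 1.5 | 3.75 | 7.5 |
| 0.40 | 0.2 | 0.8 | 2.0 | 4.0 |
| 0.40 | 0.5 | 2.0 | 5.0 | 10.0 |

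Lowest case: 100 × 0.30 × 0.2 × 0.1 = 0.6 points. Highest case: 100 × 0.40 × 0.5 × 0.5 = 10 points, which means 40 labelled patients, 20 of them negative under masked scoring, and 10 of those called positive.

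For scale, the exact (Clopper-Pearson) 95% intervals at n = 100 are:

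- 30 positive: 21.2% to 40.0%, half-width (40.0 − 21.2)/2 = 9.4 points
- 35 positive: 25.7% to 45.2%, half-width (45.2 − 25.7)/2 = about 9.7 points
- 40 positive: 30.3% to 50.3%, half-width (50.3 − 30.3)/2 = 10.0 points

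Only the most extreme case in the table reaches the half-width. Most cases are at or below half of it.

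The formula counts only upward calls among labelled patients. It leaves out any stricter scoring of patients known to have no label, which would act in the other direction. No similar calculation is possible for the Beighton score, because the documents give no distribution or rater-error figure for it.

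**The case against.** The best case against the point is that it argues from silence in a one-sentence procedure. The form is not available and may already put the physical signs first. Step 1 answers go from tablet to database, nothing routes them to the examiner, and patients who defer the questionnaire cannot inform the exam by that route. Aim 2 is descriptive and covers POTS patients only, so examiner knowledge has no group contrast to distort. The assessment uses a questionnaire as well as an exam, so the classification cannot be blind to history in any case.

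Much of this stands, and it limits what can be claimed. A reader might infer three stronger things that the documents do not support:

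- *That Step 4 has one examiner taking history and scoring signs on one form, always after Step 1.* Step 4 does not say what the form contains or who takes the history, and Step 1 may be completed up to a month later.
- *That Section 2.2 faults earlier figures for resting on reported diagnoses, so that carry-over of labels defeats the aim.* The gap it describes is under-evaluation: few geneticists specialise in EDS, and most physicians seeing POTS patients do not look for it. Examining patients with no label still addresses that gap.
- *That the reported prevalence will be inflated by a known amount.* The documents show an open route for bias. They do not show that bias occurs, or how much.

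The objection does not close the gap. Training and a standard form promote consistency but do not hide the label. Deferral is the patient's choice, and nothing bars access when answers come first. Patients who know their diagnosis can mention it whatever happens to the tablet. A descriptive percentage can be biased without any comparison group.

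**Conclusion.** The point holds as a preventable risk to a primary endpoint and to the Aim 2 percentages. It is not evidence of bias. The plan leaves the Step 4 examiner free to learn of a prior EDS diagnosis before scoring physical signs, and the existing safeguards are partial.

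Under the assumptions shown, the hEDS percentage could be raised by about 0.6 to 10 points, from negligible to about the 95% half-width at n = 100. The range depends on the cited 30-40% applying to this conference sample and on the assumed values of f and u. The effect on the Beighton score is unknown. The change is worth making because it costs little and because all POTS exams are planned around one three-day conference, so they could not easily be repeated.

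**What to change.** In Step 4 of Section 7.2:

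- State that the Beighton score and all physical signs are scored and locked before any history or prior diagnosis is taken.
- State that examiners do not open Step 1 answers before that point.
- Ask patients to hold any prior diagnosis until the history part.
- Make the hEDS/HSD classification afterwards, using history as the criteria require.

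If the standardised form already follows this order, saying so in the protocol settles that part.

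In Section 8.3, add that Beighton and hEDS/HSD results will be reported by prior-diagnosis status from Step 1. If the exams have already been done, this is the part that can still be added. It shows how closely results follow the label, but it cannot separate bias from a correct earlier diagnosis.

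The cost is the order of one form, one rule for examiners and one sentence to patients, with no extra staff. Two limits remain: some patients will still disclose, and the final classification cannot be fully masked to history.

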### 7.3 Duration of Participation

Study participation will take approximately 1 hour per subject. Subjects may opt to complete questionnaires up to 1 month after their study visit. Only POTS patients will complete questionnaires.

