# 13.0 Sharing Results with Subjects

Subjects with POTS will receive a copy of their hEDS evaluation form to discuss with their physician.

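### POTS patients who defer the questionnaires may report hEDS history after the study's own examination, and medications and fatigue that do not reflect the test day

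*Combined protocol and SAP*

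**What the plan says.** Section 7.2 makes the questionnaires Step 1, ahead of the cognitive tests (Step 3) and the hEDS/HSD evaluation (Step 4). The set has two parts. The first is history: "Subjects will answer questions about their POTS diagnosis, co-morbid conditions (including hEDS), and current medications, and family history". The second is scales: "Participants will also complete standardized questionnaires including the Orthostatic grading scale, Compass 31, RAND-36, and Fatigue-VAS".

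The order is optional, however. Step 1 adds: "Participants will have the option to complete the questionnaires during the study visit on a tablet or after their study visit". For those who choose the latter, "A link to the questionnaires in REDCap will be emailed to participants to complete after the study visit". Section 7.3 sets the limit: "Subjects may opt to complete questionnaires up to 1 month after their study visit". It also confines the questionnaires to the patient group: "Only POTS patients will complete questionnaires".

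Section 13.0 returns the examination result: "Subjects with POTS will receive a copy of their hEDS evaluation form to discuss with their physician". It does not say when.

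Section 1.3 makes questionnaire answers a secondary endpoint. Section 7.1 has questionnaire as well as examination data for Aim 2 summarised as percentages. Section 8.3 plans tests of the cognitive results only.

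**The concern.** The deferrable set mixes items that tolerate delay with items that may not. A question about existing hEDS is most useful when it refers to the time before the study examined the patient. Medication and fatigue are most useful when they refer to the day the cognitive tests were done. Once deferral is allowed, neither reference point is secured for those who take it up.

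The two problems differ. For hEDS history the delay itself does no harm, because a past diagnosis stays past. The risk is that the patient has meanwhile been examined for hEDS, may know the result, and is encouraged to take the form to a physician. A later positive answer cannot then be told apart from a diagnosis held beforehand. This contamination would run mainly one way, towards more reported prior diagnosis. For medications and the Fatigue-VAS the risk is simple mismatch: the answer may describe a different day.

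What is at stake is the questionnaire endpoint and the descriptive percentages for Aim 2. The Step 1 item is also the only medication record the protocol describes, and Sections 3.1 and 3.2 place no limit on patients' medication. A late answer therefore weakens the description of the patients whose scores Section 8.3 compares with controls.

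**Working it through.** The plan gives no figure to reproduce: Section 8.2 describes a convenience sample, and no deferral rate appears anywhere. The check is mainly one of sequence.

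1. Steps 3 and 4 are visit procedures (Section 7.2). A deferred questionnaire is answered after the visit (Step 1, Section 7.3). Every deferred answer therefore follows both the cognitive tests and the hEDS/HSD examination, by up to 1 month.
2. Nothing in the documents offsets this. No section requires medications, fatigue or prior hEDS to be recorded at the visit, asks late responders to answer as of the visit date, holds back the evaluation form until the questionnaires are in, or uses completion date in the analysis.
3. The number affected is unknown: from 0 to all of the up to 100 POTS patients (Section 8.1).

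To show what the hEDS contamination could amount to, let *p* be the true share with a prior diagnosis, *n* the share newly identified by the examination, *d* the share who defer, and *r* the share of newly identified deferrers who then report hEDS. Deferral is taken as equally common in newly identified and other patients.

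- Rise in reported prior diagnosis = *d* × *r* × *n*
- Share of newly identified cases recorded as already known = *d* × *r*

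All four inputs are assumptions. *p* = 30% is the lower end of the 30–40% that Section 2.2 cites from questionnaire studies. *n* = 15% has no source in the documents.

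| *d* | *r* | Rise | Reported prior diagnosis | Newly identified shown as known |
|---|---|---|---|---|
| 0 | any | 0 | 30% | 0% |
| 0.5 | 0.5 | 0.5 × 0.5 × 15 = 3.75 points | 33.75% | 25% |
| 0.5 | 1 | 0.5 × 1 × 15 = 7.5 points | 37.5% | 50% |
| 1 | 1 | 1 × 1 × 15 = 15 points | 45% | 100% |

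The last row is the ceiling under *n* = 15%. No similar figure can be given for medications or fatigue, because the documents say nothing about how either changes over a month.

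**The case against.** The strongest reply is that this concerns descriptive data and a deliberate feasibility choice. The primary endpoints (Section 1.2) are the cognitive scores and the Beighton score, both obtained at the visit. Section 8.3 contains no covariate model or subgroup analysis using medication or fatigue, and no aim compares newly found with known hEDS. The remark in Section 2.3 that hEDS and HSD often go unrecognised is rationale, not an estimand. The steps already add to 15 + 30 + 20 = 65 minutes against a visit of about 1 hour, so deferral relieves real pressure. The item wording and recall periods are not in the documents: the hEDS item may already ask about a prior physician diagnosis, and no reference period is given for the Fatigue-VAS. Data handling is referred to a separate form (Section 9.0), so completion dates may well be stored.

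Most of this stands, and it limits the point. A reader might infer that the questionnaire data as a whole no longer describe the patients as tested. The documents do not support that: tablet completion at the visit is available, and only deferrers are exposed. A reader might also infer that patients hold their hEDS form before they answer. That is plausible, but Section 13.0 gives no time, and Step 4 does not say that the result is told at the examination.

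The reply does not remove the point, because questionnaire answers are themselves a named secondary endpoint and Section 7.1 reports questionnaire percentages for Aim 2. The planned output is exposed without any additional analysis. Section 1.1 also assesses hEDS and HSD by a questionnaire together with an examination. Whether that questionnaire is the deferrable set is unclear; if it is, the exposure reaches the Aim 2 classification itself.

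**Conclusion.** The concern holds in a conditional form. For POTS patients who defer, self-reported hEDS may be influenced by the Step 4 examination or the returned form, and current medications and the Fatigue-VAS may not reflect the test day. The secondary questionnaire endpoint and the Aim 2 questionnaire percentages are affected; the supine-versus-standing comparison within patients and the examined Beighton score are not.

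The size is not known. The illustrative rise in reported prior hEDS, from 0 to 7.5 points at up to half deferring and to 15 points if all defer and all newly identified patients report it, rests wholly on assumed inputs and is not an estimate. It would be going too far to say that the plan biases an estimate of under-diagnosis, or that mistimed medication and fatigue data distort an analysis explaining cognition, since neither analysis is planned. The point merits a change because the change is small and because an hEDS answer uninfluenced by the examination may not be recoverable once the result is known.

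**What to change.** In Section 7.2 (Step 1) and Section 7.3:

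- Require the short history block (POTS diagnosis, co-morbidities including hEDS, current medications, family history) and the Fatigue-VAS on the tablet at the visit, before Step 3. Placing them only before Step 4 would not be enough: fatigue could then be recorded before standing in some patients and after it in others.
- Allow only the Orthostatic grading scale, Compass 31 and RAND-36 to be deferred.
- Word the hEDS item as a diagnosis held before the study visit.
- Keep the REDCap completion date, and report same-day and later scale responses separately as a check.
- State in Section 1.1 whether the Aim 2 questionnaire is part of the deferrable set.

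The cost is a split of the REDCap form and some loss of flexibility at the conference. The required items should take a few minutes of the 15 already allotted to Step 1 (the documents do not time them separately). Given that the listed steps already slightly exceed the stated visit length, keeping the longer scales deferrable preserves most of the relief.

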# 8.0 Subject Numbers and Statistical Plan

# 8.1 Number of Subjects

We will enroll up to 100 participants with Postural Tachycardia Syndrome and 50 healthy controls for this study. Subjects will participate in both aims.

### 8.2 Sample size determination

We propose to enroll up to 100 POTS patients and 50 healthy controls. We expect that this convenience sample, based on meeting attendance and recruitment feasibility, will allow for sufficient data on the prevalence of hEDS and HSD in POTS and whether cognition is affected by orthostasis in this patient population.

#### 8.3 Statistical methods

We will compare cognitive testing results by position using Wilcoxon signed-rank tests. Results will be compared between groups (POTS, controls) using Mann-Whitney U test.

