### 7.1 Study Design

For Aim 1, this study will utilize a repeated measures design in which test scores and physiological parameters will be measured at 2 different postures (supine, standing). For Aim 2, questionnaire and exam data will be reported as percentages.

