# Step 3- Orthostatic Cognitive Testing (30 minutes)

Subjects will lie down on a bed for 5 minutes. Their blood pressure will be taken in triplicate while supine. Half the subjects will perform cognitive tests (stroop word color test and identification test) before standing up. The testing will take 6 minutes (3 minutes each) and the order of the tests will be randomized. Subjects will then stand up. Blood pressure and heart rate will be taken using a brachial artery oscillometric cuff every 2 minutes. While standing, the blood pressure cuff will inflate at minutes 1, 3, 5, 7, and 9 since it takes approximately 1 minute to get the recording. After 4 minutes standing, subjects will perform cognitive tests again while standing. Subjects will remain standing for up to 10 minutes. Subjects may choose to sit down and stand again to complete testing or choose to end testing at anytime. Subjects will then lie supine for 5 minutes to recover. Half of the subjects will perform cognitive testing following recovery.

The Stroop word color test is a paper-based test and correct answers recorded by a member of the research team. This test takes approximately 3 minutes to complete. The Stroop word color test evaluates executive function. Participants will be asked to name the color of ink a word is printed in, when the word itself is a different color name. For example, subjects will be shown card with a word like "yellow" but will need to say "green" not "yellow" to answer correctly. This is difficult since we read faster than we can recognize color. This is primarily an assessment of concentration ability, but also involves executive function. In a previous study by Arnold, et al. the stroop word color test was most impaired in POTS while seated (cite the prior study). However, cognitive dysfunction in POTS linked to posture is poorly understood. It is important to assess cognitive function supine and during active standing in a large sample of POTS patients. The Identification test evaluates attention based on reaction time to correct responses to "yes or no" questions. In this study, participants will be asked "is this card red?" and then will be shown a random playing card on the tablet and press the "yes" or "no" button as quickly as possible. This test will be performed using Cogstate software on a tablet and takes approximately 3 minutes to complete.

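### Pooling both posture orders in one signed-rank test leaves any practice effect in the noise; comparing second-minus-first differences between the order groups would remove it at little cost

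*Combined protocol and SAP*

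**What the plan says.** Section 1.1 sets the question: "Hypothesis 1: Active standing in POTS worsens cognitive function". Section 7.1 describes repeated measures at two postures, supine and standing.

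Step 3 of section 7.2 gives the sequence. "Half the subjects will perform cognitive tests (stroop word color test and identification test) before standing up". Subjects then stand and are tested after 4 minutes. Next, "Subjects will then lie supine for 5 minutes to recover". Finally, "Half of the subjects will perform cognitive testing following recovery". Randomisation is stated for the order of the two cognitive tests, but not for posture order. The same step adds: "Subjects may choose to sit down and stand again to complete testing or choose to end testing at anytime".

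Section 8.1 gives the numbers: "We will enroll up to 100 participants with Postural Tachycardia Syndrome and 50 healthy controls for this study". Section 8.2 rests these on convenience and feasibility, with no power calculation.

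For analysis, section 8.3 says "We will compare cognitive testing results by position using Wilcoxon signed-rank tests" and compares POTS with controls by Mann-Whitney U. Order, period and practice are not mentioned.

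**The concern.** If every subject is to have a supine score, the two halves in section 7.2 must be different people, and the design has two posture orders. The same short tests are repeated within minutes, so the second session may be better (or worse) simply because it is second.

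The two orders balance this effect across postures, but the planned analysis does not use them. Practice pushes the standing-minus-supine difference one way in one half and the other way in the other half, and the pooled test treats that spread as random variation.

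What is at stake is power for the only stated test of Hypothesis 1. POTS recruitment is tied to one conference on fixed dates, so lost power cannot readily be bought back with more patients.

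**Working it through.** **Inputs from the documents.** Up to 100 POTS patients and 50 controls (8.1); half tested supine before standing and half after recovery (7.2); pooled signed-rank test (8.3). The documents state no power, alpha, effect size or SD, so there is no figure of the plan's own to reproduce.

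**Assumptions.** Complementary halves; two-sided 5%; normal errors; posture effect δ = 0.3; practice p from 0 to 1.0. All sizes are in SDs of the paired difference within an order group.

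**Step 1: the model.** Let D be standing minus supine.
- Supine first: D = δ + p + e.
- Standing first: D = δ − p + e.

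With equal halves the mean of D is δ, so there is no bias. The pooled variance is 1 + p².

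**Step 2: normal-theory check, n = 100.** Effective sample size is 100/(1 + p²). Approximate power is Φ(10δ/√(1 + p²) − 1.96).

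| p | effective n | 10δ/√(1 + p²) | power |
|---|---|---|---|
| 0 | 100 | 3.00 | 85% |
| 0.25 | 94 | 2.91 | 83% |
| 0.5 | 80 | 2.68 | 77% |
| 1.0 | 50 | 2.12 | 56% |

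**Step 3: the alternative.** Second minus first is p + δ + e in the supine-first group and p − δ − e in the standing-first group. The groups differ by 2δ and p drops out. With 50 per group the standard error is √(1/50 + 1/50) = 0.20, and 0.6/0.20 = 3.00 at every p. That equals the pooled value at p = 0.

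**Step 4: simulation of the rank tests** (20,000 runs per cell).

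| p | pooled, 50/50 | order-respecting, 50/50 | pooled, 25/25 | order-respecting, 25/25 |
|---|---|---|---|---|
| 0 | 82.8% | 82–83% | 52.8% | 52–53% |
| 0.25 | 80.8% | 82–83% | 50.1% | 52–53% |
| 0.5 | 75.8% | 82–83% | 42.9% | 52–53% |
| 1.0 | 50.6% | 82–83% | 20.7% | 52–53% |

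Repeat runs agree within about 1 point (for example 75.4% at n = 100, p = 0.5). At n = 100 the loss is 4.2 points at p = 0.40 and 5.5 at p = 0.45.

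**Step 5: type I error, 50/50.** At p = 0.25, 0.5 and 1.0 the pooled test rejects 4.1, 2.9 and 0.4% of the time. The order-respecting test stays at 4.7–5.3%.

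**Step 6: unequal orders at nil practice.** The standard error becomes √(1/n₁ + 1/n₂).
- 60/40: 0.6/0.204 = 2.94, power 83.6% against 85.1%, a cost of about 1.5 points. Simulation puts it at about 1–2.
- 70/30: 0.6/0.218 = 2.75, power 78.5%, a cost of about 6.6 points. Simulation puts it at about 7.

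**Step 7: the choice of order-respecting test matters.** Computing a signed-rank statistic within each order and summing does worse than pooling: 57.9% against 70.1% at p = 0.5 (n = 100, effect 0.28).

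**Step 8: comparing POTS with controls on change.** With orders 50/50 and 25/25 and an assumed difference of 0.5, the unstratified Mann-Whitney test has power 80.3, 78.0, 72.4 and 46.8% at p = 0, 0.25, 0.5 and 1.0. The van Elteren test, stratified by order, has 79–80% throughout.

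**The case against.** **The planned test is valid.** With equal halves, a significant signed-rank result can be trusted as far as additive practice is concerned, so the choice is between two valid tests. This stands, and it limits the point to efficiency.

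**The gain rests on an unknown.** No section gives a practice size. At 0.25 SD the loss is about 2 points, and no stated power target is missed. This also stands.

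**The two-order reading is inferred.** Section 7.2 describes the standing tests as a repeat, which fits only subjects already tested supine. If the two halves were the same people, the others would have no supine score and this point would not apply. Clarifying 7.2 therefore comes first.

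**The alternative is not better in every scenario.** Neither test protects against unequal carryover after the recovery period. With no posture effect and an assumed 0.2 SD residual in the post-recovery supine test, both give about 16% false positives at nil practice. At practice 0.5 SD the pooled test gives 9–13% and the order-respecting test 16%. The pooled figure is lower only because that test is conservative.

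**A stronger reading is tempting.** A reader might infer that pooling inflates type I error, since subjects may end testing early and one who stops after standing loses the pair only if tested standing first. At practice 0.25, 0.5 and 1.0 SD, pooled error is 5.1, 5.2 and 4.0% if 20% of standing-first pairs are lost (50/40), and 6.0, 8.4 and 12.6% if 30% are lost (50/35). A systematic 60/40 split gives 7.0, 11.9 and 22.3%. No section suggests imbalance of that size. Assigning order by fair coin toss would keep overall error at about 5%.

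**Conclusion.** The point holds as a matter of efficiency. On the two-order reading, the pooled test is unbiased and conservative under additive practice, and it loses power as practice grows. At n = 100 and an effect of 0.3 SD, the loss is about 2 points at practice 0.25 SD, about 7 at 0.5 SD and about 32 at 1.0 SD. It passes 5 points between 0.40 and 0.45 SD.

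These sizes are assumptions, so the documents cannot show whether the loss would be trivial or large. They also rest on equal halves, and on practice that is additive and the same in both orders. The documents do not support calling the planned analysis biased or invalid, nor the claim that the alternative is free whatever the split between orders.

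**What to change.** **Section 7.2.** State that the two halves are complementary (supine then standing, and standing then supine). Assign posture order at random in blocks, separately within POTS and within controls, and record it.

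**Section 8.3.**
- For each cognitive test, test posture within each group by a Mann-Whitney test of second-minus-first differences between the two order groups. Name this test, so that summed within-order signed-rank statistics are not used instead.
- Report complete pairs by order.
- Stratify any comparison of change between POTS and controls by order (van Elteren).
- Keep the planned signed-rank test as a sensitivity analysis if wished.
- State the assumptions: practice additive and equal in both orders, and no unequal carryover after the recovery period.

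**Cost.** A few sentences in each section, an allocation list and slightly more analysis; no extra subjects or visits. At nil practice the power cost is essentially none with near-equal orders, about 1–2 points at 60/40 and about 7 at 70/30. Blocked allocation keeps the assigned orders near equal, though not necessarily the completed pairs.
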